3. STUDY PROTOCOL

This was a multi-center, double-masked (participants and research team), randomized, placebo-controlled, phase 2/3 study conducted between January 2020 and June 2020 at 4 sites in the United States (Total Eye Care, Andover Eye Associates, Eye Research Foundation and Midwest Cornea Associates, LLC). This study (ClinicalTrials.gov identifier: NCT04343287) was performed in compliance with the ethical principles of the Declaration of Helsinki and the International Conference on Harmonisation (ICH) Harmonised Tripartite Guideline for good clinical practice (GCP). Institutional Review Board (IRB)/Ethics Committee approval was obtained. All potential subjects provided written informed consent before screening.

After the screening visit, eligible subjects entered a one-week run-in period to receive preservative-free placebo solution bilaterally three times daily (TID) to minimize the placebo effect. Subjects that exhibited improvements in symptoms of dry eye syndrome (DES) at the end of the run-in period, relative to screening values, were disqualified. Eligible subjects were subsequently randomized in a 1:1 ratio to receive placebo or BRM421 Ophthalmic Solution three times daily (TID) in each eye for total 2 weeks, and the efficacy and safety assessments were performed at 1 and 2 weeks after treatment.

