4. STATISTICAL ANALYSIS PLAN

The primary efficacy analyses, including FCS and ODS dryness, were performed using the last observation carried forward (LOCF) imputation method of the intent-to-treat (ITT) population at week 2 for missing values. The treatment effect in each group was calculated by change from baseline in pre-controlled adverse environment (CAE) mode.

The difference from baseline in pre-CAE values for active treatment was tested versus placebo using a two-way ANCOVA model adjusting for baseline at $\alpha = 0.05$. A Wilcoxon rank sum test and a two-sample *t*-test were also assessed where appropriate.

The continuous and ordinal secondary efficacy variables were analyzed with an ANCOVA model adjusting for baseline and also evaluated with a two-sample *t*-test comparing active treatment to placebo. No imputation was performed for secondary efficacy variables.

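### With no imputation and a baseline-only ANCOVA, a week 2 secondary comparison drops early leavers and leaves their week 1 values unused, which can bias it modestly if outcome-related withdrawal differs by arm

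*Combined protocol and SAP*

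**What the plan says.** All of this is in the combined protocol and SAP.

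- **Primary variables (section 4, Statistical Analysis Plan).** For FCS and ODS dryness, the section states that the analyses "were performed using the last observation carried forward (LOCF) imputation method of the intent-to-treat (ITT) population at week 2 for missing values".
- **Secondary variables (section 4).** "The continuous and ordinal secondary efficacy variables were analyzed with an ANCOVA model adjusting for baseline", and they were "also evaluated with a two-sample *t*-test comparing active treatment to placebo". On missing values: "No imputation was performed for secondary efficacy variables".
- **Visits (section 3, Study Protocol).** Treatment lasts two weeks, and "the efficacy and safety assessments were performed at 1 and 2 weeks after treatment".

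The secondary sentences name no visit, no analysis set and no list of variables. No repeated-measures term, week 1 covariate, sensitivity analysis or expected withdrawal rate appears anywhere. Week 2 is stated for the primary analyses only; applying it to the secondary variables is an inference from the primary timepoint.

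**The concern.** Take a subject who attends week 1 and then stops. In the primary analysis LOCF supplies a week 2 value, so the subject counts. In a week 2 secondary comparison by ANCOVA on baseline, the subject is deleted, and the week 1 measurement, already in the database, plays no part.

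The absence of imputation is not itself the fault, since a likelihood-based repeated-measures model does not impute either. The weakness is pairing no imputation with a method that cannot use week 1. That makes the week 2 result a completers comparison, free of bias only if, given baseline, leaving is unrelated to outcome or acts alike in both arms.

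At stake is how the secondary results are read. They are normally taken as support for the primary result, yet here they would rest on a differently selected set of subjects. Losing more poor responders from placebo would dilute a true benefit; losing more from active would inflate it.

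**Working it through.** **Plan's own figure.** The title page gives about 200 subjects, 100 per arm, randomised 1:1. No effect size, SD, power or dropout rate is given, so this cannot be reproduced. For scale, with two-sided alpha 0.05 and 80% power assumed, 100 per arm detects (1.960 + 0.842) × √(2/100) = 0.396 SD.

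**Assumptions.** The documents give none of the following: outcome SD 1, higher is worse; correlation of baseline with each later visit 0.5; week 1 to week 2 correlation r = 0.5 or 0.7; leaving after week 1 driven half by the week 1 score and half by chance (the share p with the highest week 1 score plus equal-variance noise leaves); nobody leaves before week 1.

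**Approximate bias of the completers ANCOVA.** Let S be the standardised leaving score.

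1. Mean of S among those who stay: −φ(z)/(1 − p), where z is the upper-p point of the standard normal and φ its density. For p = 2%, 5%, 8%, 12% and 15%, φ(z)/(1 − p) is 0.0494, 0.1086, 0.1616, 0.2273 and 0.2743.
2. Covariance of the baseline-adjusted week 2 outcome with S: (r − 0.5 × 0.5)/√2, which is 0.177 for r = 0.5 and 0.318 for r = 0.7.
3. Size of the bias: the covariance times the between-arm difference in step 1.

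| Withdrawal in the two arms | Difference in step 1 | Bias, r = 0.5 | Bias, r = 0.7 |
|---|---|---|---|
| 5% and 5% | 0 | 0 | 0 |
| 2% and 8% | 0.112 | 0.020 SD | 0.036 SD |
| 2% and 12% | 0.178 | 0.031 SD | 0.057 SD |
| 5% and 15% | 0.166 | 0.029 SD | 0.053 SD |

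**Simulation with the same assumptions** (100 per arm, 3000 trials per setting). With a true effect of −0.4 SD, 2% leaving active and 12% leaving placebo, the completers ANCOVA gave −0.368 (r = 0.5) and −0.338 (r = 0.7), against full-data values of −0.400 and −0.396. The shifts are 0.032 and 0.058, or 8% and 15% of the effect. Reversing the rates gives the same size in the other direction.

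**Against sampling error.** With a standard error of about 0.125, 0.03/0.125 = 0.24 and 0.06/0.125 = 0.48. The bias at a 10-point difference is therefore a quarter to a half of a standard error.

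**Type I error.** With 95 and 90 completers and baseline correlation 0.4, the standard error is √(1 − 0.16) × √(1/95 + 1/90) = 0.135. A bias of 0.05 SD then raises a two-sided 5% error rate to about 6.6%.

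**Sensitivity to the mechanism** (true effect 0).

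- A weaker logistic dependence on week 1 level gave ANCOVA bias of at most about 0.02 SD.
- Removing exactly the subjects with the worst week 1 change, at 0% versus 10%, gave 0.05 to 0.10 SD for the ANCOVA and 0.10 to 0.16 SD for a t-test on change. This is a stress case.
- A t-test on change was nearly unbiased in some level-driven settings and worse than the ANCOVA in the change-driven ones, so it is no dependable safeguard.

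**With week 1 used.** A likelihood estimate using baseline and week 1 showed no bias beyond simulation error (about 0.006 SD or less), with equal or slightly smaller standard error (for example 0.123 against 0.125). Every setting made leaving depend on observed values plus chance, which is the condition under which this model is valid.

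**The case against.** The strongest reply has four parts.

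- **The visit is inferred.** Correct, and it stands. A separate week 1 secondary analysis would still include these subjects. It is also unknown which secondary variables were measured at both visits.
- **Nothing shows that the bias occurred.** Also correct. A reader might infer that poor responders left, that one arm lost more of them, and that the secondary results are therefore wrong. The documents report no withdrawal rates, reasons or imbalance, and a masked two-week treatment period may lose few subjects. Unequal rates alone are not enough; leaving must also relate to outcome.
- **The primary analysis is no gold standard.** A reader might take LOCF as the correct benchmark. In the same kind of simulation LOCF was itself off by 0.01 to 0.09 SD, and the plan does not say what is carried forward for a subject with no post-baseline value. Disagreement between primary and secondary results could not be put down to case deletion alone, and extending LOCF to the secondary variables would not be a sound repair.
- **The remedy has limits.** Its near-zero bias depends on the assumed mechanism, and it too omits anyone without a post-baseline value.

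These points limit the size and certainty of the concern. They do not remove the feature itself: at week 2, the stated secondary methods discard a collected measurement that a standard model would use at little cost.

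**Conclusion.** The concern holds as a modest, conditional weakness. If the secondary comparison is at week 2, early leavers who were seen at week 1 are deleted from it while LOCF keeps them in the primary analysis. If leaving depends on week 1 response and the rates differ by 6 to 10 points, the ANCOVA difference is biased by about 0.02 to 0.06 SD, up to about half a standard error, in favour of the arm that loses more poor responders. With equal rates and the same mechanism it is about zero. The withdrawal rates, correlations and mechanism are all assumptions.

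The documents do not support the stronger reading that the secondary results are unreliable. They show neither substantial nor unequal withdrawal. The primary analysis and the sample size are not affected by this point.

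**What to change.** For each secondary variable measured at both weeks 1 and 2, continuous or ordinal, add a mixed model for repeated measures in all randomised subjects with at least one post-baseline value. Include treatment, visit, treatment-by-visit, baseline and baseline-by-visit, with unstructured covariance. Report the week 2 treatment difference and the number analysed per arm at each visit. Keep the observed-case ANCOVA and t-test alongside. State which visit the secondary comparisons refer to. Variables measured at one visit only keep the ANCOVA.

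The cost is a few lines of programming on data already collected, with no new visits or subjects. The downsides are:

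- The model is slightly more complex, and secondary estimates may move if withdrawal was unequal.
- It is valid only if withdrawal depends on observed data, and it does not recover subjects with no post-baseline value.
- The title page shows the study completed in June 2020 and reported in December 2020, so the added analysis must be labelled a post hoc sensitivity analysis and not presented as the planned one.

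The counts per arm and visit are worth reporting in any case. If almost nobody left between the visits, they settle the matter.
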